7.7. Data Analysis

7.7.1. Evaluation parameters

1) Case parameters

- Descriptive analysis will be performed regarding the total number of collected CRFs, the number of safety evaluation subjects, the number of efficacy evaluation subjects, the number of discontinued cases and their reasons.

2) Safety parameters

- Safety parameters will be evaluated.
- The incidence of adverse events sorted by body organ and disease/symptom
- If the data is adequate, sub-analysis can be performed for each factor that is considered to affect safety.
- Clinically significant abnormalities found in laboratory tests (if conducted)

3) Efficacy variables

- On-demand treatment
 - Responses to all the injection of the Xyntha Solofuse prefilled syringe used to treat bleeding (4 point scale: excellent, good, moderate, and no response)
 - Number of observations of less than expected therapeutic effect (LETE) (LETE: “no response” rated after each infusion of 2 consecutive infusions within 24 hours after on-demand treatment)
 - In case of bleeding: The number of infusions of Xyntha Solofuse prefilled syringes used to treat each new bleeding episode is rated.
 - Mean infusion dosage
- Prophylactic Therapy
 - Percentage of the study subjects who have experienced bleeding (overall, spontaneous)
 - Annualized bleeding rates (ABRs)
 - Number of observations of less than expected therapeutic effect (LETE)

(LETE: Atypical bleeding occurring within 48 hours after administration of the Xyntha Solofuse Prefilled Syringe by dosage for the prevention of bleeding (spontaneous/at traumatic))

- Mean infusion dosage
- Total factor consumption
- If the data are adequate, sub-analysis can be performed for each factor that is considered to affect the efficacy.

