2.2. Study Design

In this open-label, non-comparative, observational, non-interventional, retrospective and multi-center study, post-marketing surveillance data will be collected retrospectively for up to 6 months from the initial administration day of the Xyntha Solofuse prefilled syringe injected into patients who have been administered the Xyntha Solofuse prefilled syringe (as part of routine treatment at the Korean health care center which has certified investigators). If the study subject has not completed the 6-month treatment, relevant data should be collected based on the medical records within the 30 days after the last administration of the drug.

Statistical Analysis Plan for rPMS

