3.2. Efficacy Analysis Set

Efficacy analysis set will include study subjects adequate for efficacy evaluation at least once among the safety analysis set.

The following cases will be excluded from the efficacy analysis set in the following order.

- 1) Subjects who are excluded from the safety analysis set.
- 2) Subjects without efficacy assessment endpoint.
 - On-demand treatment: Responses to the injection of the Xyntha Solofuse prefilled syringe
 - Prophylactic therapy: Subjects who have experienced bleeding (overall, spontaneous)

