4) Overall efficacy assessment will be classified as effective/not-effective as follows, presented in frequency and percentage of it.

- ① On-demand treatment

- [Effective]: Subjects with whom the best responses 'Excellent' or 'Good' or 'Moderate'.
- [Not-effective]: Subjects with whom the best responses 'No response'.

- ② Prophylactic Therapy

- [Effective]: Subjects who haven't experienced any atypical bleeding within 48 hours after administration of the Xyntha Solofuse Prefilled Syringe.
- [Not-effective]: Subjects who have experienced at least once atypical bleeding within 48 hours after administration of the Xyntha Solofuse Prefilled Syringe.

5) Efficacy assessment by demographics and baseline characteristics

Classified overall assessment (effective/not-effective) will be presented in frequency and percentage based on categorical variables of demography and baseline characteristics (sex, age group, past/present disease status, renal/hepatic disorder status). To identify statistically significant difference of frequency distribution of classified overall assessment (effective/not-effective) among demography and baseline characteristics, Chi-square test or Fisher's exact

Statistical Analysis Plan for rPMS

test will be performed.

- 6) Efficacy assessment by concomitant treatment (Concomitant Treatments/Therapy status)
Classified overall assessment (effective/not-effective) will be presented in frequency and percentage for concomitant treatment status (Concomitant Treatments/Therapy status). To identify statistically significant difference of frequency distribution of classified overall assessment (effective/not-effective) among concomitant treatment status, concomitant therapy status, Chi-square test or Fisher's exact test will be performed.
- 7) Analysis of factors that affect efficacy
Logistic regression analysis of multivariate analysis will be performed and presented an odds ratio with 95% confidence interval to identify the factors that affect classified overall assessment (effective/not-effective) in demography and baseline characteristics of the patients (sex, age group, past/present disease status, renal/hepatic disorder status), or concomitant treatment status, concomitant therapy status, etc.

7. Reporting Principles

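### SAP 6.7(4) counts a prophylaxis subject who stops for lack of effect as Effective unless an atypical bleed fell within 48 hours of an infusion, and short exposure favours that label

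*SAP*

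**What the plan says.** For prophylaxis, SAP 6.7(4) has two classes. Effective is "Subjects who haven't experienced any atypical bleeding within 48 hours after administration of the Xyntha Solofuse Prefilled Syringe". Not-effective is "Subjects who have experienced at least once atypical bleeding within 48 hours after administration of the Xyntha Solofuse Prefilled Syringe". A qualifying bleed is the only route to failure.

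The other places that bear on early stopping are these:

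- **SAP 3.2.** The set is defined so: "Efficacy analysis set will include study subjects adequate for efficacy evaluation at least once among the safety analysis set". Apart from subjects already outside the safety set, the only exclusion is "Subjects without efficacy assessment endpoint". Stopping early is not a ground for exclusion.
- **SAP 2.2 (and Protocol 7.1).** The early-stop provision reads "If the study subject has not completed the 6-month treatment", and then "relevant data should be collected based on the medical records within the 30 days after the last administration of the drug". This is a data-collection window, not a scoring rule.
- **Protocol 7.7.1.** The case parameters include "the number of discontinued cases and their reasons". Section 6 of the SAP contains no table of discontinuation by reason.
- **SAP 6.5 and 6.6(2).** Duration of administration is summarised by regimen, and adverse events are tabulated by action taken, including permanent discontinuation. Neither is linked to the efficacy class.
- **SAP 6.7(5)-(7).** The Effective/Not-effective flag is the outcome for the chi-square or Fisher tests and for the logistic regression.

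**The concern.** A subject who abandons prophylaxis because it is not working is a treatment failure in the ordinary sense. Under the rule that subject is a success unless one particular kind of bleed was recorded. Bleeds later than 48 hours after an infusion do not count. Nor do bleeds not judged atypical, a term that neither document defines.

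Time under observation adds a second problem. The flag asks whether an event ever happened, so fewer infusions give fewer chances to be classed Not-effective. Both effects push the effective percentage upward.

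The report could also disagree with itself. Protocol 7.3.2.1 lists lack of efficacy among its examples of adverse events, so the same person could appear under lack of efficacy in the safety tables and as Effective in the efficacy table. Finally, a baseline factor associated with early stopping could appear associated with efficacy in 6.7(5)-(7).

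**Working it through.** The documents state no effectiveness rate, discontinuation rate or prophylaxis count, so there is no planned figure to reproduce. The check is a trace through the rules, followed by illustrations on stated assumptions.

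**1. Trace one subject.** Take a prophylaxis subject with bleeds that fell more than 48 hours after an infusion or were not judged atypical, and a recorded stop for lack of efficacy.

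- Safety set (SAP 3.1): dosed and evaluated, so included unless an inclusion, exclusion or off-label criterion applies.
- Efficacy set (SAP 3.2): bleeding data exist, so included.
- Flag (SAP 6.7(4)): no qualifying bleed, so Effective. Not-effective cannot be reached.

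The prophylaxis entry in SAP 3.2 can be read as saying that only subjects who bled have an endpoint, which would drop subjects who never bled. The traced subject did bleed and is classed Effective on either reading.

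**2. Weight of one such subject.** Moving k subjects from Effective to Not-effective lowers the percentage by 100 × k/N. Protocol section 5 gives at least 86 evaluable subjects across both regimens. The values of 60 and 30 are assumptions.

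| N on prophylaxis | k = 1 | k = 2 | k = 3 |
|---|---|---|---|
| 86 | 1.2 points | 2.3 | 3.5 |
| 60 | 1.7 | 3.3 | 5.0 |
| 30 | 3.3 | 6.7 | 10.0 |

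With 86 evaluable subjects, 1.2 points is a lower bound on the effect of one subject, because the prophylaxis group can only be smaller. If all of the roughly 95 expected subjects were evaluable and on prophylaxis, it would be 1/95 = 1.1 points.

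**3. Effect of exposure.** Assume a constant, independent chance p of a qualifying bleed per infusion, so that P(Effective after n infusions) = (1 − p)^n. Take three infusions a week, the frequency in the trial that Protocol 7.2.4 cites: 3 × 26 = 78 infusions over 26 weeks and 3 × 4 = 12 over four weeks. Assume 82/86 = 95.3% Effective at 78 infusions.

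- p = 1 − 0.953^(1/78) = 0.0006, about 0.06% per infusion.
- P(Effective after 12) = 0.953^(12/78) = 0.993, or 99.3%.
- Gap: 99.3 − 95.3 = 4.0 points.

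The gap depends on the assumed six-month figure S. With S^(m/6) for a subject stopping at month m:

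| S at 6 months | Stop at 1 month | Stop at 3 months |
|---|---|---|
| 90% | 98% | 95% |
| 70% | 94% | 84% |
| 50% | 89% | 71% |

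**4. Dilution.** Only early stoppers contribute, so the overall shift is about (share stopping) × (gap). If 10% stopped after 12 infusions, the shift is 0.10 × 4.0 = 0.4 points when S is 95.3%. If 10% stopped at one month and S were 70%, it is 0.10 × (94.2 − 70) = 2.4 points.

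**The case against.** The case for leaving the rule alone has real content.

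- **Limited consequence.** Efficacy is a secondary objective, summarised descriptively in a single-arm study with no success threshold. This stands and limits the weight of the point.
- **The information is not lost.** Bleeding proportions are reported separately, so a bleed outside 48 hours still appears there. Duration of administration is summarised. A lack-of-efficacy stop recorded as an adverse event would appear in the action-taken table. A reader might infer that the SAP ignores discontinuation altogether; it does not. None of this alters the flag, however.
- **The 48-hour gap may be small.** At three infusions a week, spaced at least 48 hours apart, the windows cover 3 × 48 = 144 of 168 hours, leaving 24 hours a week outside. This stands for a fully adherent subject on that frequency. It does not help with less frequent infusion, or with bleeds not judged atypical.
- **Events after stopping are partly captured.** A bleed within 48 hours of the last infusion counts, and the 30-day record window would find it. So it would be wrong to say that only events during treatment are scored.
- **Inhibitors.** A reader might infer that a subject who stops because of an inhibitor is scored as a success. The documents do not establish that. Criterion 4 (Protocol 7.7.2; SAP 2.3.2, applied through SAP 3.1) removes subjects with a current or suspected inhibitor. Where laboratory tests cannot be performed, it allows that judgement to rest on reduced clinical effect. It gives no time point, so such subjects, and some lack-of-effect stoppers, may be excluded instead. In neither case are they counted as failures.
- **Other scoring is defensible.** Reporting these stops as a separate category is reasonable too. The SAP should state which approach it takes.

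**Conclusion.** The point holds for the prophylaxis branch of SAP 6.7(4). As written, the rule scores a lack-of-effect stop without a qualifying bleed as Effective, if the subject remains in the efficacy set, and it favours short exposure. The direction is upward.

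The size cannot be determined from the documents. It is 1/N per such subject, plus an exposure effect that is small if qualifying bleeds are rare and larger if they are common. The exposure figures rest on a constant hazard and an assumed six-month percentage.

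Two stronger readings are not supported. One is a large bias: a 1% chance per infusion gives 0.99^78 = 46% Effective at 26 weeks, which cannot be combined with an assumed 95.3%. The other is that any factor linked to early stopping will look linked to efficacy. It may, but with few stoppers the effect could be invisible.

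The on-demand branch uses best response, "Subjects with whom the best responses 'Excellent' or 'Good' or 'Moderate", and the calculations here do not apply to it.

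**What to change.** 1. In SAP 6.7(4), add that a prophylaxis subject whose recorded reason for discontinuation is lack of efficacy is classed Not-effective. If the current rule is kept as the main analysis, make this a stated sensitivity analysis.
2. Present the effective percentage separately for subjects observed for the full six months and for those who stopped early, with the number in each group.
3. Place the discontinuation-by-reason summary required by Protocol 7.7.1 beside that table.
4. For subjects who develop an inhibitor on treatment, first reconcile criterion 4 (Protocol 7.7.2, SAP 2.3.2 and 3.1) with the efficacy set by stating the time point at which it applies. Then report these subjects separately.

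The cost is a few sentences of SAP text and one table, using reasons the protocol already calls for. The effective percentage may come out slightly lower, and splitting by completion leaves small groups.
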